10.3.2.1 Stopping Rules

- a) Full dermal thickness ulcer in any subject, of any duration;
- b) Any depth ulcer or erosion lasting ≥ 30 days, in more than 2 of the first 20 subjects treated with CellFX or more than 10% of subjects treated after the first 20 subjects; and
- c) Scab or crust that is so severe at the 30 day visit that it would preclude additional treatment that day, in more than 2 of the first 20 subjects treated with CellFX or more than 10% of subjects treated after the first 20 subjects.

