3.2 Study Design

This study is designed as a prospective, multicenter, single-blinded, randomized comparison IDE study between CellFX System and Cryosurgery. The Principal Investigator will select a sub-investigator to be the blinded investigator to classify the healing characteristics and wart clearance and/or reduction assessment of each subject's selected warts at baseline, post treatment and at 7-days, 30-days, 60-days, and 90-days following the last CellFX treatment or Cryosurgical procedure. This sub investigator will be blinded to the treatment assignment. The subject may not be blinded to the treatment assignment. The Principal Investigator can choose to be the blinded investigator and select a sub investigator to be the treating investigator.

Eligible subjects with a minimum of 2 and up to 8 warts meeting the inclusion and exclusion criteria will be enrolled. If the subject has more than 8 warts, the subject is excluded from the study. Warts may be present anywhere on the face except the scalp, nose and within the orbital region of the face. Plantar warts are also excluded. Subjects will be randomized to receive either a CellFX treatment or Cryosurgery. Selected warts for each treatment modality must be clearly separated in distance from each other so that wart treatment and side effects can be assessed by the blinded site investigator.

All eligible warts will receive at least one CellFX or Cryosurgical treatment. Each subject will be evaluated by the blinded site investigator at 7-days, 30-days, 60-days, and 90-days post-initial CellFX and Cryosurgical treatments. At the 30-day or 60-day follow-up visit, if any wart is classified as “not resolved”, the wart must receive an additional treatment. In case of a second or third retreatment, the subject will be evaluated by the blinded site investigator at 30-days, 60-days, and 90-days post-retreatment. Photography of the warts will be captured along with the blinded site investigator assessments at all visits.

Numbness (diminished/ altered sensation) Assessment: The treating investigator will conduct a “light touch” exam to all treated areas at baseline, 7 days and 30 days post initial treatment and 30 days post retreatment(s). Light touch is tested with a cotton wisp, feather, and/or even light finger touch. The subject will be asked how one area feels compared to another.

Note 1:

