4.4 Schedule of Events and Evaluations

Schedule of events and evaluations required for this study are provided in **Table 2**.

Table 2: Schedule of Events

Study Activity/ Procedure	Visit 1 Enrollment 1 st TX	Visit 2 7-days Post- 1 st TX	Visit 3 30-days Post- 1 st TX	Visit 4 60-days Post- 1 st TX	Visit 5 90-days Post- 1 st TX	Visit 6 120-days Post- 1 st TX	Visit 7 150-days Post- 1 st TX
	Visit Range	±3 days	±10 days	±10 days	±10 days	±10 days	±10 days
	Consent / Wart Eval / Tx 1	Wart Eval	Wart Eval / Tx 2	Wart Eval / Tx 3	Wart Eval / Final Visit Subject Satisfaction	Wart Eval / Final Visit Subject Satisfaction	Wart Eval / Final Visit Subject Satisfaction
Informed Consent	✓						
Demographics, Medical HX, Fitzpatrick Skin Type, Baseline Wart Size	✓						
Photographs of Non-treated Warts	✓				✓	✓	✓
Subject Randomization	✓						
1 st TX (CellFX or Cryosurgery)	✓						
2 nd TX (CellFX or Cryosurgery)			✓ If required				
3 rd TX (CellFX or Cryosurgery)				✓ If required			
Photographs of Pre and Post Treated Warts	✓	✓	✓	✓	✓	✓	✓
Wart Healing Characteristics	✓	✓	✓	✓	✓	✓	✓
Assessment of Numbness in the Treated Area	✓	✓	✓	✓*	✓*		
Wart Clearance/Resolution			✓	✓	✓	✓	✓
Wart Reduction Assessment		✓	✓	✓	✓	✓	✓
Pain Score/ Assessment for muscle twitching: Treated Warts	✓		✓	✓			
6 Point Subject Satisfaction Scale (SSS)					✓	✓	✓
Adverse Event Assessment	✓	✓	✓	✓	✓	✓	✓
Study Exit					✓	✓	✓

*Numbness assessment will be performed at Visit 4 for those subjects who are retreated at the 30 day follow up visit.

*Numbness assessment will be performed at Visit 5 for those subjects who are retreated at the 60 day follow up visit.

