- Photographic images of all treated warts will be taken with pre- and post-wart markings
- All warts will be clinically assessed by the blinded site investigator (wart healing characteristics, wart clearance and wart reduction assessments)
- Assessment of numbness in the treated area will be performed by the treating investigator

- If any wart is classified as “not resolved”, a second treatment with CellFX or Cryosurgery will be performed to the previously treated wart(s)

In case of a second CellFX or Cryosurgical treatment is required:

- Local anesthesia/numbing will be applied to each wart designated for a CellFX retreatment
- Each wart designated for a CellFX retreatment will be treated using pre-determined energy settings
- Each wart designated for Cryosurgical retreatment will be performed as outlined in protocol **Section 3.5**
- The subject will be asked to rate his/her pain immediately after each wart treated with CellFX and/or Cryosurgery by using a numerical rating score
- The subjects will be asked whether they felt muscle twitching immediately after each lesion treated with CellFX
- Immediately post-procedure, a wart healing characteristics assessment will be performed by the blinded site investigator
- Photographic images of all retreated warts will be taken post-treatment
- A light bandage and/or any physician recommended dressing may be applied before the subject leaves the clinic
- Any adverse events will be identified and documented with a live assessment by the blinded site investigator

4.8 60-Day Follow-up Visit (CellFX/Cryosurgical Treatment #3, if required)

- Photographic images all treated warts will be taken with pre- and post-wart markings
- All warts will be clinically assessed by the blinded site investigator (wart healing characteristics, wart clearances and wart reduction assessments)
- Assessment of numbness in the treated area will be performed by the treating investigator (only for those subjects who received a retreatment at the 30-day follow-up visit)

- If any wart is classified as “not resolved”, a third treatment with CellFX or Cryosurgery will be performed to the previously treated wart(s)

In case of a third CellFX or Cryosurgical treatment is required:

- Local anesthesia/numbing will be applied to each wart designated for a CellFX retreatment
- Each wart designated for a CellFX retreatment will be treated using pre-determined energy settings

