6.4 Populations for Analyses

The primary analysis dataset for study outcomes will be the intent-to-treat (ITT) population wherein data from all randomized warts will be analyzed based on the intended randomization assignment. The intent of this protocol is to apply up to 3 sessions of each treatment, but no warts will be

excluded from the ITT population based on the number of treatments actually received. The primary efficacy analysis will be performed using the ITT population. A modified intent-to-treat population will include all warts that received at least one treatment, and the primary efficacy analysis will also be calculated for this population for comparison. The modified ITT population will be the analysis population for the primary safety endpoint.

Study outcomes will also be analyzed using a per-protocol (PP) population. The PP population includes all subjects who had no pre-specified inclusion and exclusion violations, received either CellFX or Cryosurgery, and repeated the treatments per protocol for any warts classified as “not resolved” at the 30-day and/or 60-day visit.

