10.3.2 Safety Monitor

The Sponsor will select an independent Safety Monitor to oversee dermatological adverse events. The First 20 subjects who are treated with CellFX will have their data analyzed when they complete the 30 day follow up visit or 30 days post initial treatment. A table describing the 30 days status of the subjects will be prepared. Adverse events will be presented as the percentage of subjects who experience an event, the number of events and the event rate per 30 days. The photographic images of the dermatological adverse events will also be presented to the Safety Monitor.

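### Stopping rule (c) names only the 30-day visit, so a treatment-precluding scab or crust at the 60-day visit, after a second CellFX exposure, most naturally falls outside the trigger

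*Combined protocol and SAP*

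**What the plan says.** Section 10.3.2.1 has three stopping rules.

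- Rule (a): one full-thickness ulcer in any subject, however brief.
- Rule (b): an ulcer or erosion of any depth that persists for 30 days or longer. It is met above 2 of the first 20 CellFX subjects, or above 10% of those treated later. No visit is named.
- Rule (c): a "Scab or crust that is so severe at the 30 day visit that it would preclude additional treatment that day", with the same two thresholds.

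Retreatment is decided on two occasions. Section 3.2 sets them: "At the 30-day or 60-day follow-up visit", a wart that is not resolved has to be treated again. Section 4.7 places treatment 2 at the 30-day visit and Section 4.8 places treatment 3 at the 60-day visit. Three treatments is the maximum.

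The protocol generally uses the 30-day label for Visit 3. Section 10.3.2, which contains the stopping rules, says that the first 20 CellFX subjects "will have their data analyzed when they complete the 30 day follow up visit or 30 days post initial treatment". A Table 2 footnote reads "Numbness assessment will be performed at Visit 4 for those subjects who are retreated at the 30 day follow up visit", which keeps Visit 4 apart from the 30-day visit. Section 6.4 defines the per-protocol population by retreatment "at the 30-day and/or 60-day visit".

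**The concern.** Rule (c) asks whether the skin has healed enough to be treated again on the day when retreatment is due. There are two such days, and the rule names one. The omitted day is the one that follows a second CellFX exposure, and repeat exposure is a required part of the regimen for unresolved warts. If slow healing appears mainly after repeated treatment, the rule designed to detect it would not respond.

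What is at stake is a formal pause-and-review trigger during the trial. The co-primary endpoints, the sample size and the type I error rate do not depend on it.

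**Working it through.** **1. Which decision visits the rules cover**

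| Decision visit | CellFX exposures so far | Precluding scab or crust under (c) | Under (a) or (b) |
|---|---|---|---|
| 30-day (Visit 3, treatment 2) | 1 | counted | no, ulcers and erosions only |
| 60-day (Visit 4, treatment 3) | up to 2 | not counted on the natural reading | no, ulcers and erosions only |

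After treatment 3 there is no further treatment to preclude, so the 60-day visit is the only decision visit left out.

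**2. How much counting the 60-day visit would matter**

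The protocol gives no operating characteristic for rule (c), so there is no figure to reproduce. The following is an illustration.

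Inputs:

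- q, the chance that a subject has a precluding scab or crust at a decision visit after CellFX. The documents do not give it; 2%, 5% and 10% are assumed, equal at both visits.
- r, the share of subjects retreated at the 30-day visit, also assumed. Two figures in Section 1.5 give a range.
  - Lower end: in the earlier pivotal study, overall efficacy is reported on 93 common warts and single-treatment efficacy on 63. If the difference is read as retreated warts, 30/93 = 0.323. With warts within a subject fully correlated, r = 0.323.
  - Upper end: in the feasibility study, 19 of 37 treated warts had two treatments. With 3 warts per subject (Section 6.3) and independence, r = 1 − (18/37)³ = 0.885.

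Formulas:

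- 30-day visit only: p = q.
- Both visits, each subject counted once, visits independent: p = q + (1 − q) × r × q.
- Rule met in the first 20: P(X ≥ 3), with X binomial (20, p).

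| q | 30-day visit only | Both visits, r = 0.323 | Both visits, r = 0.885 |
|---|---|---|---|
| 2% | 0.7% | p = 0.0263: 1.5% | p = 0.0373: 3.7% |
| 5% | 7.5% | p = 0.0653: 13.9% | p = 0.0920: 27.8% |
| 10% | 32.3% | p = 0.1290: 48.7% | p = 0.1796: 72.4% |

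The increase runs from about 1.5-fold (48.7/32.3) to about 5-fold (3.7/0.7).

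**3. Harm that appears only after a second exposure**

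On the Visit 3 reading, rule (c) can then never be met. With the 60-day visit counted and half of subjects retreated (assumed), p = 0.5 × risk. A risk of 10%, 20% or 30% among retreated subjects gives 7.5%, 32.3% or 59.5%.

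**4. Age of the wound at the 60-day visit**

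Table 2 allows ±10 days, so Visit 3 falls on Day 20 to 40 and Visit 4 on Day 50 to 70. The gap from treatment 2 to Visit 4 is therefore 10 to 50 days. Of 21 × 21 = 441 permitted day pairs, 55 (12%) leave under 20 days. Visit 3 itself is never earlier than Day 20, so a 20-day minimum puts both visits on the same footing.

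**The case against.** **The wording may already cover it.** Section 3.2 says that retreated subjects are evaluated 30 days after retreatment. For a subject treated at Visit 3, Visit 4 is that evaluation, so the rule's 30-day wording could be read to include it. This is possible but weaker: Section 10.3.2 ties the 30-day visit to the initial treatment, and Table 2, Section 3.2 and Section 6.4 name the two visits separately. A stopping rule should not leave the choice open.

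**It was meant as an early look.** Section 10.3 describes an early assessment of the first 20 CellFX subjects, and a 60-day count arrives late. Assume even enrolment of 150 over 3 to 4 months and 1:1 allocation. The first 20 CellFX subjects are in after 40/150 of that time, 0.8 to 1.07 months. Their 60-day visits end about 2 months later, when 2.8/3 = 93% or 3.07/4 = 77% of subjects are enrolled. So the value as an early stop is modest. But rule (c) also has a limb for subjects treated after the first 20, and a trigger at that point could still halt remaining treatments.

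**Detection is in place.** Section 10.3.1 has a live safety assessment at every visit and three-day reporting of events related to the stopping rules. Table 4 has three-day reporting of adverse device effects. Section 3.2 records reasons for missed retreatment, and a Safety Monitor oversees dermatological events. All of this stands. It provides detection, not a numerical trigger.

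**Two looks at a one-look threshold mean more stops.** This stands as a cost. Keeping the thresholds is still consistent with rule (b), which uses the same limits with no visit restriction.

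**Conclusion.** The gap is real and minor. On the most natural reading, a precluding scab or crust at the 60-day visit does not count toward rule (c), and no other stopping rule covers it. This rests on the text alone.

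The sizes are illustrative. The per-visit risk is assumed. The lower retreatment share comes from subtracting two denominators that the protocol does not link. The upper share mixes common and plantar warts. Positive correlation between a subject's two visits would make the increase smaller than shown.

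Two stronger conclusions should not be drawn. A reader might infer that slow healing after repeat CellFX treatment would go unseen; the visit-by-visit assessment and reporting duties contradict that. A reader might also infer that rule (b) has the same fault, because the first-20 table is prepared at Visit 3, when an ulcer may not yet have lasted 30 days. Rule (b) is not tied to that visit and can be met later, so no defect is shown there.

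**What to change.** In Section 10.3.2.1(c), replace the reference to the 30-day visit with: *at the 30-day or 60-day visit, at least 20 days after the most recent CellFX treatment*. State that each subject is counted once, and keep both thresholds.

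The change needs no new visit, data field or subject, and no endpoint or analysis is altered. The cost is that rule (c) will be met more often, including when the true risk is low, by the illustrative amounts above. The 20-day minimum keeps scabs younger than any counted at Visit 3 out of the tally; without it the 60-day count could include wounds only 10 days old.

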10.3.3 Investigator Responsibilities

The Investigator is responsible for reporting adverse events, including device malfunctions and device deficiencies as defined in the protocol. **Table 4** summarizes the time sensitive requirements for reporting adverse events and device deficiencies. The Sponsor is the contact person for these reporting requirements.

Table 4: Investigator Responsibilities for Submitting Adverse Events to the Sponsor

Type of Adverse Event	Reporting Timeframe
*Serious Adverse Device Effects (SADE), including Unanticipated Serious Adverse Device Effect (USADE) and dermatological events as described in section 9.3.2.1	As soon as possible, but in no case later than 3 calendar days after the clinical site first learns of the event or of new information in relation with an already reported event
**Serious Adverse Events (SAE)	As soon as possible, but in no case later than 3 calendar days after the clinical site first learns of the event or of new information in relation with an already reported event
Adverse Device Effects (ADE)	As soon as possible, but in no case later than 3 calendar days after the clinical site study team first learns of the event or of new information in relation with an already reported event
All other AEs	Submit in a timely manner after the clinical site first learns of the event

Type of Adverse Event	Reporting Timeframe
**Device Deficiency with SADE potential	As soon as possible, but in no case later than 3 calendar days after the clinical site study team first learns of the deficiency or of new information in relation with an already reported deficiency
All other Device Deficiencies	Submit in a timely manner after the clinical site first learns of the deficiency

*The Sponsor will report the results of an evaluation of an unanticipated serious or serious adverse device effect to the FDA and all reviewing IRBs and investigators within 10 working days after the Sponsor first received notice of the adverse effect per 21 CFR 812.150.

**It is the responsibility of the investigator to inform their IRB of serious adverse events and device deficiencies as required by their IRB guidelines.

11.0 STUDY MANAGEMENT (SPONSOR RESPONSIBILITIES)

11.1 Sponsor Ethical and Regulatory Considerations

As the Sponsor of this clinical study, Pulse Biosciences has the overall responsibility for the conduct of the study, including assurance that the study meets US federal and local regulatory requirements appropriate to the conduct of the study and is conducted according to the Declaration of Helsinki, Protection of Human Volunteers (21 CFR 50), Institutional Review Boards (21 CFR 56), and Obligations of Clinical Investigators (21 CFR 312). The study sponsor will adhere to sponsor general duties as described in ISO 14155:2011, Clinical investigation of medical devices for human subjects – Good clinical practice, and CFR Part 812, 50, 56, 54 and the World Medical Association Declaration of Helsinki.

To maintain confidentiality, all evaluation forms, reports, and other records will be identified by a unique subject identification code (ID number). All study records will be kept in a locked file cabinet and clinical information will not be released without written permission of the subject, except as necessary for monitoring by the FDA. The Investigator must also comply with all applicable privacy regulations (e.g., Health Insurance Portability and Accountability Act of 1996).

General Duties

Pulse Biosciences will ensure that the application is submitted to the appropriate regulatory authorities, obtaining copies of IRB approvals and ensuring documentation of IRB approvals prior to the shipping of devices, ensuring proper clinical site monitoring, ensuring patient informed consent is obtained, providing quality data that satisfies regulations and informing the Investigators and IRBs of unanticipated adverse device effects, events, and deviations from the protocol as appropriate.

11.2 Selection of Clinical Sites

The primary requirements of site and Investigator selection and continued participation in the Trial include adequate experience, commitment to safety, consistency in adherence to the protocol, and patient volume. The clinical site must have facilities that are capable of processing patients in the manner prescribed by the protocol.

The study sponsor, Pulse Biosciences, and its designees will select qualified Investigators, ship, or deliver devices only to participating Investigators, obtain signed study agreements, and provide Investigators with the information necessary to conduct the study.

11.3 Site Training

The training of appropriate clinical site personnel will be the responsibility of the Sponsor designee. The Investigator is responsible for ensuring that his/her staff conduct the study according to the protocol. To ensure proper device usage, uniform data collection, and protocol compliance, the Sponsor or designee will present a formal training session to study site personnel which will review the Instructions for Use of the device, the Investigational Plan, instructions on data collection, schedules for follow-up with the study site coordinators, and regulatory requirements. Detailed feedback regarding completion of forms will be provided by the Sponsor or designee through the regular site monitoring.

11.4 Investigator Training

The Sponsor will provide appropriate Investigator training on the use of the CellFX System, Handpiece, and Treatment Tips. Training will take place prior to the initiation of the clinical investigation. Training will address topics including indications for use of the device, management of complications, and instructions to subjects. Training will be documented for each physician on a training log, signed by both the physician and training representative.

All treating investigators will be required to watch a training video on how to perform the Cryosurgical procedure for this study.

Canfield Scientific, Inc. will provide training to the sites on the photography equipment and services as described in **Section 8.0**.

11.5 Monitoring of Study Sites

11.5.1 Monitoring Methods

Monitoring functions for this study will be conducted by Pulse Biosciences. The study will be monitored to ensure that the protocol, applicable regulations, and Good Clinical Practice Guidelines are followed. The study monitor will ensure that the rights and well-being of subjects are protected, and the clinical trial data are accurate, complete, and verifiable. Specific monitoring requirements are detailed in the study specific Monitoring Plan.

Prior to subject enrollment, the Sponsor will obtain the essential regulatory documents required to initiate the study. The Sponsor will be responsible for the review and approval of the following essential documents:

- Current Protocol Revision
- Investigator Agreement
- IRB approval letter for the protocol and consent form
- IRB approved consent form
- IRB membership roster or assurance number

Copies of file documents will be maintained by the Sponsor.

